5.3. Important protocol deviation not leading to elimination from per-protocol analysis set

Important protocol deviations not leading to elimination from PPS are defined in MALARIA-073 Protocol Deviation Management Plan.

6. STATISTICAL ANALYSES

Note that standard data derivation rule and stat methods are described in Section 11 and will not be repeated below.

All statistical analyses will be performed using SAS 9.2 or later versions.

6.1. Demography

6.1.1. Analysis of demographics/baseline characteristics planned in the protocol

Demographic characteristics (age, gender, length for age Z-score, and weight for age Z-score) of each cohort (ES and PPS for immunogenicity) will be tabulated per study group.

The mean age at first vaccination [Vitamin A administration for Control group] (in months, 1 decimal digit) (plus range and standard deviation) of the vaccinated subjects, as a whole, and per group, will be calculated.

6.1.2. Additional considerations

Demographic characteristics, cohort description, withdrawal status will be summarized by group using descriptive statistics:

- Frequency tables will be generated for categorical variables such as gender.
- Mean, median, standard deviation, minimum and maximum will be provided for continuous data such as age.
- The withdrawal status will be summarized by group using descriptive statistics.
- The number of subjects enrolled into the study as well as the number of subjects excluded from PPS analyses will be tabulated.
- The numbers of withdrawn subjects will be tabulated according to the main reason for withdrawal.

6.2. Exposure

6.2.1. Analysis of exposure planned in the protocol

The number and percentage of subjects who received study vaccine doses will be tabulated for each study group (ES).

6.2.2. Additional considerations

Not Applicable.

6.3. Efficacy/Effectiveness

6.3.1. Analysis of efficacy planned in the protocol

Not Applicable.

6.3.2. Additional considerations

Not Applicable.

6.4. Immunogenicity

6.4.1. Analysis of immunogenicity planned in the protocol

The primary analysis will be based on the PPS for immunogenicity.

For the primary endpoint, the 95% CIs of the anti-CS GMT ratio between the groups (RTS,S group over Coad group) at one month post Dose 3 of RTS,S/AS01_E will be calculated. Non-inferiority of anti-CS immune response will be concluded if the UL of this CI is below 2.

For the secondary endpoints, the 95% CIs of the difference in anti-Me, anti-Ru and anti-YF seroconversion/seropositivity rates between the groups (Control group minus Coad group) at one month post-vaccination will be calculated (standardized asymptotic). The seroconversion rate is defined as the percentage of initially seronegative that are seropositive post-vaccination. Non-inferiority will be concluded if the UL of this CI is below 10%.

The percentage of subjects with seropositive levels of anti-CS (proportion of subjects with anti-CS antibody titres ≥ 1.9 EU/ml) with 95% CI will be determined at Day 0 and one month post Dose 3 of RTS,S/AS01_E in the RTS,S group and Coad group. Antibody titres will be summarized by GMT with 95% CI. Antibody titres at one month post Dose 3 of RTS,S/AS01_E will also be investigated using reverse cumulative curves.

Seroprotection level for anti-HBs with 95% CI will be determined at Day 0 and one month post Dose 3 of RTS,S/AS01_E in the RTS,S group and Coad group. Anti-HBs titres will be summarized by GMT with 95% CI. Anti-HBs titres one month post Dose 3 of RTS,S/AS01_E will also be investigated using reverse cumulative curves.

Seropositivity levels of anti-Ru (≥ 4 IU/ml) and seropositivity levels of anti-Me (≥ 150 mIU/ml) with 95% CI will be determined pre-vaccination and one month post-vaccination with the YF vaccine and the combined measles and rubella vaccine in the Control group and Coad group. Antibody titres will be summarized by GMT with 95% CI. Anti-Ru and anti-Me titres at one month post-vaccination with the YF vaccine and the combined measles and rubella vaccine will also be investigated using reverse cumulative curves.

Seropositivity levels of anti-YF (≥ 10 ED50) with 95% CI will be determined one month post-vaccination with the YF vaccine and the combined measles and rubella vaccine in the Control group and Coad group. Antibody titres will be summarized by GMT with 95% CI. Anti-YF titres at one month post-vaccination with the YF vaccine and the combined measles and rubella vaccine will also be investigated using reverse cumulative curves.

For the tertiary endpoints, the anti-catalase concentrations will be summarized by seropositivity and geometric mean concentration with 95% CI at Day 0 (Control and Coad groups), at one month post Dose 3 of RTS,S/AS01_E in the Coad group and before administration of the first dose of RTS,S/AS01_E in the Control group.

6.4.2. Additional considerations

Standard data derivation procedures for immunogenicity are available in Section 11 (see Section 11.2.4).

The primary analysis will be based on the PPS cohort for analysis of immunogenicity. If, the percentage of vaccinated subjects with serological results excluded from the PPS cohort for analysis of immunogenicity is 5% or more, a second analysis based on the ES will be performed to complement the PPS analysis.

Statistical methods for Geometric Mean Titres/Concentrations and GMT ratio

Within group assessment

GMTs and GMCs and associated two-sided 95% CIs will be computed for each group and for each strain at each available immunogenicity monitoring (see Section 6.4– Immunogenicity monitoring). The 95% CI for the mean of log-transformed titre (or concentration) will be first obtained assuming that log-transformed titres (or concentrations) are normally distributed with unknown variance. Logarithmic transformations use base 10. The 95% CI for the GMT (or GMC) will then be obtained by exponential transformation (base 10) of the 95% CI for the mean of the log-transformed titres (or concentrations).

Between group assessment

The group GMT ratio (RTS,S group over Coad group) of anti-CS at one month post Dose 3 of RTS,S/AS01_E will be obtained using an ANOVA model on the logarithm-transformed titres. The ANOVA model will include the study group as fixed effect. The GMT ratio and its two-sided 95% CI will be derived as exponential-transformation (base 10) of the corresponding group contrast in the model.

Reverse cumulative distribution curves

Reverse cumulative distribution (RCD) curves for antibody titres will be plotted: the x-axis represents the antibody titres value (log-10 scale), while the y-axis the percentage of subjects having a log-transformed antibody value greater or equal to the corresponding x-value. RCD curves analysis is performed by study group for the following immunogenicity monitoring:

- one month post Dose 3 of RTS,S/AS01E for anti-CS and anti-HBs titres
- one month post-vaccination with the YF vaccine and the combined measles and rubella vaccine for anti-Me, anti-Ru and anti-YF titres

Statistical methods for seropositivity/seroprotection rates and for seroconversion/seropositivity rates differences

The percentage of subjects seropositive/seroprotected and associated two-sided 95% Clopper-Pearson confidence intervals (CIs) will be computed by vaccine group for each strain at each available immunogenicity monitoring. In addition, differences in percentages (for seroconversion rates of anti-Me and anti-Ru and for the seropositivity rate of anti-YF at one month post-vaccination) between the groups (Control group minus Coad group) will be calculated and the associated confidence interval for the difference will be constructed using the method of Miettinen and Nurminen.

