5.2.2.2.1. Study group and treatment number allocation

The target will be to enroll approximately 700 eligible subjects who will be randomly assigned to three study groups in a (1:1:1) ratio (approximately 233 subjects in each group).

Allocation of the subject to a study group at the investigator site will be performed using a randomization system on internet (SBIR). The randomization algorithm will use a minimization procedure accounting for center.

After obtaining the signed and dated ICF from the subject's parents/LAR(s) and having checked the eligibility of the subject, the site staff will access SBIR. Upon providing the subject identification number, the randomization system will determine the study group and will provide the treatment number for the products to be administered at Visit 2 (Day 0).

The number of each administered vaccines must be recorded in the eCRF on the Vaccine Administration screen.

When SBIR is not available, please refer to the SBIR user guide or the Study Procedures Manual (SPM) for specific instructions.

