10.4. Determination of sample size

For the primary endpoint, with 205 evaluable subjects per group the study has at least 90% power to rule out a minimum 2-fold decrease in anti-CS GMTs in the Coad group versus the RTS,S group with a 2-sided 5% alpha level and an assumed anti-CS log standard deviation of ≤ 0.9 (see [Table 19](#)).

For the secondary endpoints, the power to demonstrate non-inferiority in terms of anti-YF, anti-Ru and anti-Me with 205 evaluable subjects per group is presented in [Table 19](#). Non-inferiority is defined as the UL of the 95% CI on the difference (Control group minus Coad group) in response $<10\%$.

In order to account for drop-outs and subjects non-evaluable for immunogenicity endpoints (approximately 12%), 233 subjects per group will be enrolled for a total of 699 subjects.

Table 19 Sample size and power

Antibody	Endpoint	Non-inferiority limit	Reference in control	Power
Anti-CS	GMT ratio (RTS,S group / Coad group)	2-fold decrease	log SD ≤ 0.9	90%
Anti-Ru	Seroconversion	10%	90%*	90%
Anti-YF	Seropositivity	10%	95%**	99%
Anti-Me	Seroconversion	10%	90%**	90%

Power of a non-inferiority test on seroconversion/positivity or means, 2-sided alpha 0.05, N=205 (Pass 2005).

* Adapted from Rubella vaccines: WHO position paper [[WHO](#), 2011].

** [[GlaxoSmithKline Biologicals Clinical Study Report Amendment 1 - 106369](#) (MALARIA-050)].

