13. ANNEX 3: STUDY SPECIFIC MOCK TFL

The following drafted study specific mocks will be used.

The data display, title and footnote is for illustration purpose and will be adapted to the study specificity as indicated in the TFL TOC. These templates were copied from MALARIA-063 and additional tables required for public disclosure were added.

Note that there may be few changes between the study specific SAP mock TFL and the final TFLs as editorial/minor changes do not require a SAP amendment.

Template 1 Number of subjects enrolled by center, per study group (Exposed Set)

Center	Coad N =		RTS,S N =		Control N =		Total N =	
	n	%	n	%	n	%	n	%
PPD (Ghana)								
PPD (Ghana)								

Coad =

RTS,S =

Control =

N = Number of subjects

n = Number of subjects enrolled by center

Center = GSK Biologicals assigned center number

% = n / Number of subjects with available results x 100

Template 2 Number of enrolled subjects by country (All Enrolled Set)

Country	Coad N =	RTS,S N =	Control N =	Total N =
	N	n	n	n
Ghana				

Coad =

RTS,S =

Control =

N = number of subjects

n= number of enrolled subjects included in each group or in total

Template 3 Number of enrolled subjects by age category (All Enrolled Set)

Characteristics	Categories	Coad N =	RTS,S N =	Control N =	Total N =
		n	n	n	n
Age category	Infants and toddlers (28 days-23 months)				

Coad =

RTS,S =

Control =

N = Number of enrolled subjects

n= number of enrolled subjects included in each group or in total for a given age category or for all age categories

Missing = <describe missing>

Template 4 Consort, per study group (Month 4.5)(all screened set)

	Total	Coad	RTS,S	Control
Screened				
Reasons for not being vaccinated				
Did not meet eligibility criteria				
Migrated/Lost to FU before first vaccination				
Other				
Protocol violation				
Vaccinated (at least one vaccination)				
Reasons for incomplete vaccination course				
Other				
Protocol violation				
Serious adverse event				
Subjects with full vaccination course				
Reasons for elimination from PPS for immunogenicity				
Serological results not available				
Administration of concomitant vaccination				
Wrong replacement				
Inclusion criteria not met				
Out of interval				
PPS for immunogenicity				

Coad =

RTS,S =

Control =

Template 5 Number of subjects vaccinated, completed and withdrawn with reason for withdrawal until Month 4.5, per study group (Exposed Set)

	Coad	RTS,S	Control	Total
Number of subjects vaccinated				

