N = Number of times each eligibility criterion was reported as a reason for a subject failing screening

Note: Subjects could fail multiple eligibility criteria. Therefore, the sum of N in this table is greater than the number of subjects that were screening failures due to not meeting the eligibility criteria

LAR : Legally Acceptable Representative

ICF : Informed Consent Form

Template 13 Primary objective assessment: Non-inferiority assessment of anti-CS antibody response to RTS,S/AS01E in Coad and RTS,S groups, GMT ratio, Month 4 (Per-Protocol Set)

Antibody	RTS,S		Coad		GMT ratio (RTS,S / Coad)		
	N	GMT	N	GMT	Value	LL	UL
Anti-CS							

RTS,S =

Coad =

GMT = geometric mean antibody titre

N = Number of subjects with post-vaccination results available

95% CI = 95% confidence interval for the GMT ratio (Anova model - pooled variance); LL = lower limit, UL = upper limit

PIII(M4) = Post Dose 3, Month 4

Template 14 Non-inferiority assessment of anti-Me and anti-Ru antibody seroconversion rates in Coad and Control groups, Differences, Month 4 (Per-Protocol Set)

							Difference in seroconversion rate (Group 1 minus Group 2)			
							95 % CI			
Antibody	Group 1	N	%	Group 2	N	%	Difference	%	LL	UL
Anti-Me	Control			Coad			Control - Coad			
Anti-Ru	Control			Coad			Control - Coad			

Control =

Coad =

N = number of subjects with available results

% = percentage of subjects with Anti-Me/Anti-Ru titre \geq . MIU-ML post-vaccination and $<$.MIU-ML pre-vaccination

95% CI = 95% Standardized asymptotic confidence interval; LL = lower limit, UL = upper limit

P_{III}(M4) = Post Dose 3, Month 4

Template 15 Non-inferiority assessment of anti-YF antibody seropositivity rate in Coad and Control groups, Difference, Month 4 (Per-Protocol Set)

						Difference in seropositivity rate (Group 1 minus Group 2)			
						95 % CI			
Group 1	N	%	Group 2	N	%	Difference	%	LL	UL
Control			Coad			Control - Coad			

Control =

Coad =

N = number of subjects with available results

% = percentage of subjects with Anti-YF titre \geq . MIU-ML

95% CI = 95% Standardized asymptotic confidence interval; LL = lower limit, UL = upper limit

P_{III}(M4) = Post Dose 3, Month 4

Template 16 Anti-CS seropositivity rates and GMTs in Coad and RTS,S groups, Month 4 (Per-Protocol Set)

			≥ 1.9 EU/ml				GMT					
			95% CI						95% CI			
Antibody	Group	Timing	N	n	%	LL	UL	value	LL	UL	Min	Max
Anti-CS	RTS,S	Pre										
		P _{III} (M4)										
	Coad	Pre										
		P _{III} (M4)										

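### Allocation is minimised on centre but the primary anti-CS model omits centre, so the GMT-ratio interval is somewhat too wide if centre predicts titre; adding centre costs almost nothing

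*SAP*

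**What the plan says.** Protocol 5.2.2.2.1 describes the allocation: "The randomization algorithm will use a minimization procedure accounting for center". Centre is the only factor it names, and allocation is 1:1:1.

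For the primary comparison, SAP 6.4.2 (Between group assessment) fits an ANOVA to log-transformed Month 4 anti-CS titres: "The ANOVA model will include the study group as fixed effect". The GMT ratio and its interval "will be derived as exponential-transformation (base 10) of the corresponding group contrast in the model". The footnote to Template 13, the mock primary table, agrees: "95% confidence interval for the GMT ratio (Anova model - pooled variance", with no covariate named.

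Protocol 10.8 and SAP 6.4.1 name no covariate either. SAP section 9 lists one change from the planned analyses, the anti-CS seropositivity threshold. In the SAP, centre serves only for an enrolment count (Template 1).

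**The concern.** Minimising on centre makes the centre mix nearly the same in each group, so differences between centres largely cancel from the RTS,S/Coad contrast. A model with group alone does not know this. It counts between-centre variance as residual noise and reports a standard error that is too large whenever centre predicts titre.

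The primary conclusion rests on one upper confidence limit being below 2. An interval that is too wide cannot make a false claim of non-inferiority more likely. It can only cost precision, and it means that the stated 95% coverage is not what the method delivers.

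**Working it through.** **Inputs.** From protocol 10.4: 205 evaluable per group, log SD at most 0.9, two-sided alpha 5%, about 12% non-evaluable, 233 enrolled per group. From SAP 6.4.1: margin 2, which is log10(2) = 0.3010. Assumed, because the documents do not give them: the share R² of log10-titre variance due to centre, and the number of centres. Mock Template 1 shows two rows, which is only illustrative.

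**The plan's own figures.**
- Unadjusted SE = 0.9 × √(2/205) = 0.0889.
- Power at a true ratio of 1 = Φ(0.3010/0.0889 − 1.96) = Φ(1.426) = 92.3%, which meets the stated 90%.
- Enrolment = 205/0.88 = 233.

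**Effect of leaving centre out.**
- Centre-adjusted SE = 0.0889 × √(1 − R²).
- True SE of the unadjusted contrast = 0.0889 × √(1 − R² + 0.12 R²). Allocation balances centre, and 12% random loss before the per-protocol set lets 12% of the centre variance back in.
- Excess width of the unadjusted interval = 1/√(1 − R²) − 1.
- Largest observed ratio that passes = 2/10^(1.96 × SE).
- Fold gap between two equal centres = 10^(2 × 0.9 × √R²).

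Coverage, one-sided error and power use the reported SE of 0.0889 against the true SE. For R² = 10%, the true SE is 0.0849, so unadjusted power = Φ((0.3010 − 1.96 × 0.0889)/0.0849) = 93.2%. The adjusted SE is 0.0843, so adjusted power = Φ(0.3010/0.0843 − 1.96) = 94.6%.

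| Centre share R² | GMT gap, two equal centres | Unadjusted CI wider by | Unadjusted coverage | Unadjusted one-sided error | Power, unadjusted vs adjusted | Largest passing ratio, adjusted |
|---|---|---|---|---|---|---|
| 0 | none | 0% | 95.0% | 2.5% | 92.3 vs 92.3% | 1.339 |
| 2.8% | 2-fold | 1.4% | 95.3% | 2.4% | 92.6 vs 93.0% | 1.347 |
| 5% | 2.5-fold | 2.6% | 95.5% | 2.3% | 92.8 vs 93.5% | 1.353 |
| 10% | 3.7-fold | 5.4% | 96.0% | 2.0% | 93.2 vs 94.6% | 1.367 |
| 20% | 6.4-fold | 11.8% | 96.9% | 1.5% | 94.2 vs 96.6% | 1.397 |

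Without adjustment the largest passing ratio is 1.339 in every row.

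**Simulation.** The set-up was 699 children in three arms, biased-coin minimisation on centre (probability 0.8, assumed), 12% random loss and 30,000 data sets per scenario.
- For shares of 5, 10 and 20%, the group-only one-sided error was 2.3, 2.0 and 1.6% with two centres, and 2.3, 1.9 and 1.7% with ten.
- With centre in the model, the error stayed at 2.4–2.6% and coverage at 94.8–95.2%.
- With three centres and a 10% share, the group-only error was 1.9% under minimisation but 2.5% under simple randomisation. The conservatism therefore comes from balancing on centre and then omitting it.

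**Cost when centre is irrelevant.** One degree of freedom is lost per extra centre, out of 2 × 205 − 2 = 408. Ten extra centres change the t multiplier from 1.96580 to 1.96594, or 0.0075%. Simulated power changed by about 0.1 point or less. With ten centres and no centre effect, the mean ratio of upper to lower limit was 2.2396 with centre and 2.2365 without.

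**The case against.** The strongest reply is that nothing here is an error. The interval errs on the safe side, the power claim holds, and no document promises a covariate. The premise is also unsupported. The documents report no centre effect, and the design limits some sources of one: a one-month age window at first dose, enforced visit intervals, and a single designated laboratory for anti-CS. The larger gains need centre GMTs further apart than the 2-fold margin. With two equal centres, a 1.5-fold gap gives power of 92.4 against 92.5%. Moreover, 0.9 is the protocol's ceiling for the SD: at SD 0.7, a 2-fold gap gives 99.3 against 99.4%. A centre-adjusted sensitivity analysis might then be enough.

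The points about size stand. The benefit is conditional and probably small, and the cost is negligible rather than literally zero. They do not remove the mismatch between design and analysis. Exposure to malaria, for one, could still differ between centres. A sensitivity analysis would show the gain but could not be used for the primary decision, and in an open-label trial adding centre after seeing the data would look post hoc.

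**Conclusion.** The point holds as a recommended improvement, not as a validity fault. Allocation uses centre and the primary model does not. If centre predicts titre, the interval is conservative, by 2.6 to 11.8% in width for assumed centre shares of 5 to 20%; the 20% row is an upper extreme. The gain in power runs from zero to about 2.4 points. The non-inferiority conclusion would change only if the observed ratio fell in a narrow band just above 1.34. These figures assume SD 0.9, 205 evaluable per group, near-exact balance on centre at allocation, and loss unrelated to group or titre. The fold gaps further assume two equal centres.

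**What to change.** In SAP 6.4.2, fit log10 Month 4 anti-CS on study group plus centre, both as fixed effects, and take the RTS,S/Coad ratio and its 95% interval from the centre-adjusted group contrast. Keep the group-only ANOVA as a sensitivity analysis, and amend the Template 13 footnote to match. If centre is left out on purpose, SAP 6.4.2 should say why.

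The cost is one sentence, one model term and one footnote; centre is already recorded.

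Centre-stratified Miettinen–Nurminen intervals for the seroresponse differences are optional. With two equal centres at 85 and 95%, or 90 and 100%, R² = 0.05²/[p(1 − p)] = 0.028 or 0.053, and the narrowing 1 − √(1 − R²) is only about 1.4% or 2.7%.

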6.5. Analysis of safety

6.5.1. Analysis of safety planned in the protocol

The primary analysis will be based on the ES.

The percentage of subjects with at least one local AE (solicited and unsolicited), with at least one general AE (solicited and unsolicited) and with any AE during the solicited follow-up period [7 days post Dose 1, post Dose 2 and 14 days post Dose 3] will be tabulated with exact 95% CI after each vaccine dose and overall. The percentage of doses followed by at least one local AE (solicited and unsolicited), by at least one general AE (solicited and unsolicited) and by any AE will be tabulated for the overall vaccination course, with exact 95% CI. Similar tables will be generated for Grade 3 AEs and AEs considered as causally related to vaccination.

The percentage of subjects reporting each individual solicited local and general AE during the solicited follow-up period will be tabulated with exact 95% CI. The percentage of doses followed by each individual solicited local and general AE will be tabulated for each dose and for the overall vaccination course, with exact 95% CI. Similar tables will be generated for Grade 3 AEs, causal events and for fever, temperature in 0.5°C increments.

The proportion of subjects reporting an AE (unsolicited) until 30 days (Days 0-29) post each dose of RTS,S/AS01_E, classified by the Medical Dictionary for Regulatory Activities (MedDRA) preferred term level will be tabulated with exact 95% CI. The proportion of subjects reporting an AE (unsolicited) until 42 days (Days 0-41) after the administration of the YF vaccine and the combined measles and rubella vaccine (restricted to the Coad group and Control group), classified by the MedDRA preferred term level will be tabulated with exact 95% CI. Similar tables will be generated for Grade 3 AEs and AEs considered as causally related to vaccination.

The proportion of subjects reporting an SAE (all, fatal, related) occurring within 30 days (day of vaccination and 29 subsequent days) after each visit where a study product is potentially administered, classified by the MedDRA preferred term level will be tabulated with exact 95% CI.

The proportion of subjects reporting an SAE (all, fatal, related) from Day 0 to Month 4.5 and over the whole study duration (Day 0 to Month 33 for Coad and RTS,S groups and Month 36 for the Control group), classified by the MedDRA preferred term level will be tabulated with exact 95% CI.

The proportion of subjects reporting an AEs of specific interest (pIMDs, meningitis and seizures) from Day 0 to Month 4.5 and over the whole study duration (Day 0 to Month 33 for Coad and RTS,S groups and Month 36 for the Control group), classified by the MedDRA preferred term level will be tabulated with exact 95% CI.

For generalized convulsive seizures occurring within 7 days after vaccines administered at Visit 2 and 3 (Coad and RTS,S groups) and 14 days after vaccines administered at Visit 4 (all groups) an analysis will be performed based on the Brighton Collaborations guidelines [**Bonhoeffer**, 2004]. This includes descriptive tables of the time relationship of seizures to vaccination, the duration of seizures and the level of diagnostic certainty.

